## REVISION HISTORY

### Revisions to Version 2.0

Date: 15 Mar 2023

## 2 LIST OF ABBREVIATIONS AND DEFINITIONS OF TERMS

Abbreviation	Term
ADI	actual dose intensity
AE	adverse event
AF	allelic frequency
AI	aromatase inhibitor
ALP	alkaline phosphatase
ALT	alanine aminotransferase
ANC	absolute neutrophil count
AST	aspartate aminotransferase
ATC	Anatomical Therapeutic Chemical
AUC	area under the concentration-time curve
AUC (0-inf)	AUC from zero time extrapolated to infinite time
AUC (0-t)	AUC from zero time to time of last quantifiable concentration
BP	blood pressure
BSAP	bone-specific alkaline phosphatase
CxDx	cycle (CxDx = Cycle x Day x)
cfDNA	cell-free DNA
CL/F	apparent total clearance following oral administration
C max	maximum observed concentration
CR	complete response
CRF	case report form
CTC	circulating tumor cells
CTCAE	Common Terminology Criteria for Adverse Events
CTX	C-terminal cross-linking telopeptide of type 1 collagen
DBP	diastolic blood pressure
DCR	disease control rate
DET	double endometrial thickness
DLT	dose-limiting toxicity
DOR	duration of response

Abbreviation	Term
ECOG PS	Eastern Cooperative Oncology Group Performance Status
EOT	end of treatment
ER	estrogen receptor
ER $\alpha$	estrogen receptor alpha
ESR1	estrogen receptor 1 gene
HR	heart rate
FAS	full analysis set
MedDRA	Medical Dictionary for Regulatory Activities
MTD	maximum tolerated dose
NCI CTCAE	National Cancer Institute Common Terminology Criteria for Adverse Events
ORR	objective response rate
OS	overall survival
PD	pharmacodynamic(s)/disease progression
PFS	progression-free survival
PG	pharmacogenetic(s)
PgR	progesterone receptor
PINP	amino-terminal propeptide of type 1 collagen
PK	pharmacokinetic(s)
PO	orally
PR	partial response
PT	preferred term
Q1, Q3	first quartile, third quartile
QD	once daily
QTcF	QT interval corrected for heart rate using Fridericia's formula
Rac	accumulation ratio
RECIST	Response Evaluation Criteria in Solid Tumors
RP2D	recommended phase 2 dose
RES	response evaluable set
RR	respiratory rate

Abbreviation	Term
SAE	serious adverse event
SAP	statistical analysis plan
SAS®	Statistical Analysis System
SBP	systolic blood pressure
SD	stable disease
SI	Système International
SOC	system organ class
SSC	Study Steering Committee
StD	standard deviation
TEAE	treatment-emergent adverse event
t max	time at which the highest drug concentration occurs
ULN	upper limit of normal
V Z/F	apparent volume of distribution at terminal phase
WBC	white blood cell/white blood cell count
WHO DD	World Health Organization Drug Dictionary

### 3 INTRODUCTION

The purpose of this statistical analysis plan (SAP) is to describe the procedures and the statistical methods that will be used to analyze and report results for Eisai Protocol H3B-6545-A001-101, Amendment 09, dated 29 August 2022: A Phase 1-2 multicenter, open-label trial of H3B-6545, a covalent antagonist of estrogen receptor alpha, in women with locally advanced or metastatic estrogen receptor-positive, HER2 negative breast cancer.

#### 3.1 Study Objectives

##### 3.1.1 Phase 1 Primary Objective

The primary objective of the Phase 1 portion of this study is to:

- Determine the maximum tolerated dose (MTD) and/or the recommended Phase 2 dose (RP2D) of H3B-6545 in women with locally advanced or metastatic estrogen receptor-positive, HER2-negative breast cancer.

##### 3.1.2 Phase 1 Secondary Objectives

The secondary objectives of the Phase 1 portion of this study are to:

- Evaluate the safety and tolerability of H3B-6545 as a single agent administered orally (PO) once daily (QD) over a 28-day cycle in this subject population.
- Characterize the plasma pharmacokinetics (PK) of H3B-6545.
- Estimate the efficacy of H3B-6545 in terms of response rate, duration of response (DOR), disease control rate (DCR), progression-free survival (PFS) and overall survival (OS).

##### 3.1.3 Phase 1 Exploratory Objectives

The exploratory objectives of the Phase 1 portion of this study are to:

CC1

### 3.1.4 Phase 2 Primary Objective

The primary objective of the Phase 2 portion of this study is to:

- Estimate the efficacy of H3B-6545 in terms of best overall response rate, DOR, DCR, clinical benefit rate (CBR), PFS, and OS in with (ER)-positive, HER2-negative breast cancer and in those with and without estrogen receptor alpha (ER $\alpha$ ) mutation (including a clonal *ESR1* Y537S mutation).

### 3.1.5 Phase 2 Secondary Objectives

The secondary objectives of the Phase 2 portion of this study are to:

- Further characterize the safety of H3B-6545 in this patient population.
- Further characterize the PK of H3B-6545. At least sparse PK samples will be collected from all patients on study.
- Evaluate the effect of a high-fat meal on the relative bioavailability of H3B-6545.
- Assess the effect of H3B-6545 on serum bone turnover markers, namely bone-specific alkaline phosphatase (BSAP), for osteoclast metabolism; amino-terminal propeptide of type 1 collagen (PINP), for bone formation; and C-terminal cross-linking telopeptide of type 1 collagen (CTX), for bone resorption.
- Assess the effect of H3B-6545 on endometrial thickness and uterine volume. This objective will be assessed in a subgroup of women with intact uteri.

### 3.1.6 Phase 2 Exploratory Objectives

The exploratory objectives of the Phase 2 portion of this study are to:

CC1

[figure not shown]

## 3.2 Overall Study Design and Plan

This is a first-in-human, multi-center, open-label, dose-escalation followed by dose expansion Phase 1/2 study of H3B-6545 for women with ER-positive, HER2-negative, locally advanced or metastatic breast cancer. The study contains a Phase 1 dose escalation part, and a Phase 2 dose expansion portion as shown below:

- The Phase 1 dose escalation part will follow a standard 3+3 cohort design to determine the MTD/RP2D. Once a subject has completed Cycle 3 at her assigned dose level of drug, intra-subject dose escalation will be allowed.

- The Phase 2 dose expansion part will examine the efficacy of the RP2D. Two substudies are included to examine the food effect on PK and effect of H3B-6545 on the endometrium. In addition, approximately [REDACTED] subjects having a clonal *ESR1* Y537S mutation, in the absence of *ESR1* D538G mutation are enrolled to examine the efficacy.

Abbreviations: DL=dose level; ER $\alpha$ mut=estrogen receptor alpha mutant; ER $\alpha$ WT=estrogen receptor alpha wild-type; MTD=maximum tolerated dose; PK=pharmacokinetics; PO=orally (by mouth); QD=once daily; RP2D=recommended Phase 2 dose.

All subjects entering this study will receive H3B-6545 PO once daily. Efficacy, safety and PK/PD will be assessed according to the Schedule of Assessments (Protocol Appendix E). Subjects are permitted to continue treatment with H3B-6545 until disease progression, unacceptable toxicity, or decision to discontinue treatment by the subject or the study physician. After discontinuation from protocol treatment, subjects must be followed for adverse events (AEs) for 28 days after their last dose of study drug. If a subject discontinues therapy for a reason other than disease progression, they will continue to be evaluated for response until disease progression or until they start a new anti-cancer therapy. Following disease progression, all subjects will be followed for survival at least every 12 weeks, and survival follow-up will end 6 months after the last subject receives their first dose of study treatment (at the time of data cutoff for the primary analysis) (as of Amendment 9), and no survival follow-up will be done in the Extension Phase.

The primary analysis for efficacy will be based on data collected 6 months after the last subject receives their first dose of study treatment.

## 4 DETERMINATION OF SAMPLE SIZE

### 4.1 Phase 1

CCI

[figure not shown]

### 4.2 Phase 2

In the Phase 2 portion of the study, for subjects enrolled prior to Amendment 06, Simon two-stage design (Simon, 1989) will be used in evaluating the response rate in the response evaluable set (RES, defined in Section 5.2.1). Subjects in the Phase 1 part who were treated at the RP2D and were deemed evaluable, will be included in the RES. CCI

CCI

#### 4.2.1 Sample size calculation for the Phase 2 food-effect sub-study

CCI

#### 4.2.2 Sample size calculation for the endometrium sub-study

CCI

## 5 STATISTICAL METHODS

As of CCI the RP2D of H3B-6545 has been determined as CCI

Three sets of analysis will be performed, including subjects from both Phase 1 and Phase 2 portions of the study, which also includes subjects enrolled under Amendment 06.

Presentation by treatment group: grouping by starting dose levels will be applied to all analyses, unless specified otherwise. The default analysis set is full analysis set (**FAS**, [defined in Section 5.2.1](#)) for all analysis, and response evaluable set (**RES**, [defined in Section 5.2.1](#)) will be applied to selected analysis of response rate.

Presentation by baseline *ESR1* mutation groups: grouping by *ESR1* mutation groups (per sponsor approved laboratory analysis of cfDNA) will be applied to selected efficacy and safety analysis. The default analysis set is FAS subjects who started on CCI with known *ESR1* status.

For presentation by baseline *ESR1* mutation groups, the following definitions are used to define the mutation groups per sponsor approved laboratory analysis of cfDNA, only including subjects with known *ESR1* status:

- **Clonal Y537S** consists of all subjects who receive at least 1 dose of study drug, carry *ESR1* Y537S at a mutation AF  $\geq 0.5\%$ , and do not carry *ESR1* D538G at an AF  $\geq 0.5\%$ .
- **Clonal D538G** consists of all subjects who receive at least 1 dose of study drug, carry *ESR1* D538G at an AF  $\geq 0.5\%$ , and do not carry *ESR1* Y537S at an AF  $\geq 0.5\%$ .
- **Clonal Y537S or clonal D538G** consists of all subjects who are either clonal Y537S or clonal D538G, defined above.
- **Polyclonal Y537S and D538G** consists of all subjects who receive at least 1 dose of study drug and carry both *ESR1* Y537S at an AF  $\geq 0.5\%$  and *ESR1* D538G at an AF  $\geq 0.5\%$ .
- **Y537S and D538G negatives** consists of all subjects who receive at least 1 dose of study drug and carry neither *ESR1* Y537S at an AF  $\geq 0.5\%$  nor *ESR1* D538G at an AF  $\geq 0.5\%$ .

All descriptive statistics for continuous variables will be reported using mean, standard deviation (StD), median, the first quartile (Q1), the third quartile (Q3), minimum and maximum. Categorical variables will be summarized as number (percentage) of subjects. In addition, all data will be presented in subject data listings unless otherwise specified.

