## 5.2 Study Subjects

### 5.2.1 Definitions of Analysis Sets

Analyses will be performed using the following analysis sets:

- **Full Analysis Set (FAS)**, which will consist of all subjects who receive at least 1 dose of study drug.
- **FAS with Known *ESR1* Status**, which will consist of all subjects who receive at least 1 dose of study drug and have known *ESR1* status per sponsor approved laboratory analysis of cfDNA. Subjects with unknown *ESR1* status will be excluded. This analysis set will be used for two types of analysis:
  - Analysis by *ESR1* mutation groups: clonal Y537S, clonal D538G, clonal Y537S or clonal D538G, polyclonal Y537S and D538G, Y537S and D538G negatives
  - Analysis by *ESR1* mutation status: mutant versus wild type: *ESR1* mutant group includes any mutation at an AF  $\geq 0.05\%$  (ie, limit of detection); *ESR1* wild type group include any mutation at an AF  $< 0.05\%$ .
- **Safety Analysis Set**, which will consist of all subjects who receive at least 1 dose of study drug. This will be the analysis set for all safety evaluations except DLT results.
- **Dose Evaluable Set**, which will consist of all subjects who were evaluable for DLT in Cycle 1 of Phase 1, as collected on case report form (CRF) page. This will be the analysis set for DLT results. Note that subjects who do not receive study drug for at least 70% of the planned dose of H3B-6545 during the first cycle (28 calendar days) for reasons not considered to be a DLT by both the investigators and the Sponsor will be replaced; the subjects who are replaced will not be considered evaluable for DLT assessments ([Protocol Section 10.11.5](#)).
- **PK Analysis Set**: This analysis set will be derived and reported in a separate PK analysis report.
- **Food-effect Analysis Set**: This analysis set will be derived and reported in a separate PK analysis report.

CC1

- **Response Evaluable Set (RES)**, which will consist of those subjects who receive at least 1 dose of study drug and have measurable disease at baseline and at least 1 post-baseline adequate evaluation. This will be the primary analysis set for efficacy evaluations.
- **Endometrium Safety Evaluable Set**, which will consist of those subjects with intact uteri at baseline, who receive at least 1 dose of study drug and have ultrasound assessments at screening/baseline and three months after starting trial therapy.

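### Do the two ESR1 cut-offs, 0.5% for the mutation groups and 0.05% for mutant status, make the ESR1 analyses contradict each other?

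*SAP*

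**What the plan says.** Section 5 defines five baseline ESR1 mutation groups from cfDNA, all at AF 0.5%. Clonal Y537S means Y537S at or above 0.5% and D538G not at or above 0.5%. Clonal D538G is the mirror image. A third group pools these two. Polyclonal means both variants at or above 0.5%. The negative group "consists of all subjects who receive at least 1 dose of study drug and carry neither *ESR1* Y537S at an AF" of at least 0.5%, nor D538G at that level.

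Section 5.2.1 defines the FAS with known ESR1 status and states: "This analysis set will be used for two types of analysis". The first is by mutation group, as above. The second is by mutation status, where the "mutant group includes any mutation at an AF" of 0.05% or more, which the SAP identifies as the limit of detection. Subjects below that are wild type.

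Section 3.2, the design overview, mentions "subjects having a clonal *ESR1* Y537S mutation, in the absence of *ESR1* D538G mutation are enrolled to examine the efficacy" and gives no AF limit there. Section 3.1.4 makes efficacy with and without ERα mutation, including clonal Y537S, part of the Phase 2 primary objective.

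**The concern.** The two cut-offs differ tenfold (0.5 / 0.05 = 10) and apply to the same analysis set. Anyone with Y537S or D538G between 0.05% and 0.5% has a detected variant that the mutation groups treat as not carried. Such a subject can appear as mutant in one efficacy table and as negative in another. A subject in the clonal Y537S group can also have detectable D538G, although Section 3.2 speaks of its absence.

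If that were a defect, two things would be at stake. The mutation groups would not be what their names suggest, in a trial whose Phase 2 primary objective refers to them. Low-AF carriers among the negatives, and D538G carriers among the clonal Y537S subjects, would also make the group estimates look more alike than they should.

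**Working it through.** **Inputs.** The group cut-off is 0.5%, for Y537S and D538G only (Section 5). The status cut-off is 0.05%, for any ESR1 mutation (Section 5.2.1). The SAP gives no AF distribution, so there is no stated figure to reproduce.

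**Step 1: classify example profiles under both rules.**

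| Y537S | D538G | Other ESR1 | Status (0.05%) | Group (0.5%) | Group if cut at 0.05% |
|---|---|---|---|---|---|
| 0 | 0 | 0 | wild type | negative | negative |
| 0.3% | 0 | 0 | mutant | negative | clonal Y537S |
| 0.6% | 0.4% | 0 | mutant | clonal Y537S | polyclonal |
| 2.0% | 2.0% | 0 | mutant | polyclonal | polyclonal |
| 0 | 0 | 2.0% | mutant | negative | negative |

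Rows 2 and 3 are the cases complained of. In row 3, D538G is at 0.4 / 0.05 = 8 times the limit of detection.

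**Step 2: look for a contradiction.** A wild-type subject has every AF below 0.05%, hence below 0.5%, and is always in the negative group. A clonal or polyclonal subject has at least one variant at 0.5% or more, hence above 0.05%, and is always mutant. The schemes therefore nest. The negative group equals the wild-type subjects plus mutant subjects whose Y537S and D538G are both below 0.5%. No subject is wild type in one analysis and a carrier in the other.

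**Step 3: ask whether the cut-off causes the overlap.** Row 5 is mutant and negative whichever common cut-off is used, because mutant status covers any ESR1 mutation while the negative group covers two named variants. A common cut-off would remove row 2 but not row 5. The group's label names those two variants and does not claim that a subject is free of ESR1 mutation.

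**Step 4: check that the groups are well formed.** Each of the two variants is either at or above 0.5% or below it. The 2 × 2 combinations are clonal Y537S, clonal D538G, polyclonal and negative, so these four groups are exclusive and exhaustive. The fifth is the union of the first two.

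Now suppose absence meant AF below 0.05% while presence still meant 0.5% or more. A subject with Y537S at 20% and D538G at 0.06% would then be neither clonal, polyclonal nor negative. A separate low-AF category would put that subject beside one whose only finding is Y537S at 0.1%.

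**Step 5: see where the groups are used.** Efficacy by mutation status, at the limit of detection, is the comparison named in Section 5.3.4 and the protocol-defined subgroup in Tables 1 and 2. It counts low-AF carriers as mutant. The mutation groups receive estimates (Sections 5.4.1 and 5.4.2). Covariate adjustment and multiplicity are marked not applicable (Sections 5.3.2 and 5.3.3), and no test between the groups is visible. The visible Table 1 row for the later hypothesis test takes the response-evaluable subjects dosed under or after Amendment 6 as a single group.

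**Step 6: try to size the dilution.** Let p be the proportion with detectable Y537S or D538G, and s the share of those below 0.5%. The share of carriers among the negatives is p·s / (1 − p + p·s). Both p and s are assumptions.

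- AF log-uniform from 0.05% to 50%: s = ln(0.5/0.05) / ln(50/0.05) = 1/3. For p = 20%, 30% and 40% this gives 0.0667/0.8667 = 7.7%, 0.1/0.8 = 12.5% and 0.1333/0.7333 = 18.2%.
- s = 10%: 0.02/0.82 = 2.4%, 0.03/0.73 = 4.1% and 0.04/0.64 = 6.3%.

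The range reflects only what is assumed, and it does not translate into a change in ORR or PFS.

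**The case for a change.** The best case for the concern is about names and reasons. The visible text does not say why 0.5% was chosen. A reader who sees clonal or negative without a footnote may take it to mean that the other variant was not detected. Section 3.2 speaks of absence with no AF limit. The wild-type definition is also loosely worded: taken literally, it describes subjects who have a mutation below 0.05%, not subjects with none.

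These observations are accurate, but they do not carry the concern. Section 3.2 is a design summary, and Section 5 supplies the operational rule. The enrolment criterion belongs to the protocol, which is not at hand. If eligibility was judged at 0.5%, a stricter rule for absence would remove correctly enrolled subjects from their own cohort. An analyst would read an undetected variant as below 0.05%, so the wild-type wording is a clerical matter.

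The tables can also be related to each other. Section 5.2.4 summarises ESR1 mutation status at baseline by mutation group for subjects who started on 450 mg, and Section 5.4.1 promises a listing of efficacy data that includes ESR1 mutation status. Neither is promised to separate low-AF Y537S or D538G from other ESR1 variants, so that detail may remain unseen. Parts of the subgroup, biomarker and table text are redacted, so a missing rationale or low-AF analysis cannot be asserted.

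**Conclusion.** The concern does not hold. The tenfold difference is real, and the 0.05% to below 0.5% band is classified as described. It results from two separately named analyses with explicit rules, 0.5% being used throughout Section 5 and 0.05% for mutant status. The rules can be programmed and nest without conflict, and the four basic mutation groups form a complete partition. The broad question of efficacy with and without mutation is already answered at the limit of detection.

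Setting absence at the limit of detection instead would be a defensible preference, but it would leave some subjects without a group and would not remove the overlap caused by other ESR1 variants. The size of any dilution is unknown: 2% to 18% of the negative group under assumptions that the SAP neither supports nor excludes. This conclusion rests on the visible text, in which no test between the mutation groups appears. A redacted decision rule that used them would be a reason to look again.

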### 5.1 Study Endpoints

#### 5.1.1 Phase 1 Primary Endpoint

The primary study endpoint for Phase 1 is the occurrence of dose limiting toxicity (DLT) as a function of the dose of H3B-6545 for determination of the MTD and/or RP2D.

### 5.1.2 Phase 1 Secondary Endpoints

[figure not shown]
Secondary study endpoints for Phase 1 are:

- Safety/tolerability: the type and frequency of AEs and serious AEs (SAEs) using National Cancer Institute Common Terminology Criteria for Adverse Events (NCI CTCAE) v4.03, as well as changes in clinical laboratory values, vital sign measurements and ECG parameters.
- PK: standard primary PK parameters including, but not limited to, the area under the concentration-time curve from zero time to time of last quantifiable concentration ( $AUC_{(0-t)}$ ), maximum observed concentration ( $C_{max}$ ), time at which the highest drug concentration occurs ( $t_{max}$ ), and accumulation ratio ( $R_{ac}$ ).
- Preliminary efficacy: Response will be determined by the investigator assessments. The following endpoints will be determined:
  - Objective response rate (ORR), defined as the proportion of subjects achieving a best overall response (BOR) of confirmed partial or complete response (PR + CR).
  - Duration of response (DOR), defined as the time from the date of first documented and confirmed CR/PR until the first documentation of disease progression as determined by the investigator or death, whichever comes first.
  - Disease control rate (DCR), defined as the proportion of subjects achieving a best overall response of CR, PR, or stable disease (SD).
  - Progression-free survival (PFS), defined as the time from first dose date to the date of the first documentation of disease progression as determined by the investigator or death (whichever occurs first).
  - Overall survival (OS), defined as the time from first dose date to the date of death (event) or date last known alive or data cutoff date, whichever comes first (censored).

### 5.1.3 Phase 1 Exploratory Endpoints

Exploratory study endpoints for Phase 1 include:

CCI

### 5.1.4 Phase 2 Primary Endpoint

The primary study endpoint for Phase 2 is ORR, defined as the proportion of subjects achieving a BOR of confirmed PR + CR.

Response will be determined by the investigator assessment according to Response Evaluation Criteria in Solid Tumors (RECIST) 1.1 ([Protocol Appendix F](#)). Detailed rules for deriving BOR are provided in [Appendix 13.1](#). Note that BOR of SD has to be achieved at least  $\geq 7$  weeks after the first dose. All response of CR and PR must be confirmed by repeated scans  $\geq 4$  weeks following the initial achievement of response.

Additional efficacy endpoints (determined by investigator assessment):

- Duration of response (DOR), defined as the time from the date of first documented and confirmed CR/PR until the first documentation of disease progression as determined by the investigator or death, whichever comes first.
- Disease control rate (DCR), defined the proportion of subjects achieving a best overall response of CR, PR, or SD. Note that Non-CR/non-disease progression (PD) will be included for subjects without measurable lesion at baseline ([Appendix 13.1](#)).
- Progression-free survival (PFS), defined as the time from first dose date to the date of the first documentation of disease progression as determined by the investigator or death (whichever occurs first).
- Overall survival (OS), defined as the time from first dose date to the date of death (event) or date last known alive or data cutoff date, whichever comes first (censored).
- Clinical benefit rate (CBR): defined as the proportion of subjects with BOR of CR, PR, or durable SD (duration of SD  $\geq 23$  weeks). For subjects whose BOR is SD, duration of SD is defined as the time from the date of first dose to the date of the first documentation of disease progression or death, whichever occurs first. Note that for subjects without measurable lesion at baseline, timepoint response of Non-CR/non-PD will be considered as SD for analysis purpose ([Appendix 13.1](#)).

